5.2 Treatment assignment

We designed a two-stage randomization process to study both direct treatment and spillover effects of health insurance.

In a first stage, we randomly assigned villages to one of five village-level arms. A village-level arm is defined by the percentage of households within the village assigned to each of the four household-level study arms defined in subsection 4.2.1. The percentage allocations to the 4 household-level arms are given in the last 4 columns of Table 1. The percent of villages assigned to each of the 5 village-level arms are in the second column. Villages were matched before this first stage randomization.⁷

Table 1: IHIE Two-Stage Randomization Design

Village-level arms (%)		Household-level arms (%)			
Arm	Village allocation	Group A	Group B	Group C	Group D
I	15	30	50	10	10
II	15	30	10	50	10
III	15	30	10	10	50
IV	35	70	10	10	10
V	20	10	30	30	30
Total	100	40	20	20	20

In a second stage, we randomly assigned households within a village to the four arms according to the allocation probabilities assigned to the village. Households were matched before this second stage randomization.⁸

The target enrollment for each of the 4 household-level arms, unconditional on village-level arm, was 4,500 households for condition A and 2,250 households for each of conditions B, C and D. Due to some attrition between listing and completion of baseline, our final randomized sample amounted to 11,089 households in 424 villages in the two districts.

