5.4 Treatment Delivery

The population that is eligible for this study would not be eligible for RSBY under the program's usual rules. To make this study possible, we exchanged letters of cooperation with the state in which we conducted the study (Karnataka), the central government agency (Ministry of Labor) responsible for administration of RSBY, and the development organization (GIZ) providing technical support for RSBY.

Sample households were randomized in August 2014 using data from the listing exercise. They were informed of their treatment assignment and, depending on which arm to which they are assigned, given access to insurance or cash in May and June 2015. This step took place roughly 18 months after the baseline due to government constraints. Due to challenges associated with evaluating a government program, we were only able to enroll sample households when the government held its RSBY enrollment drive in early 2015.

We enrolled study households much in the same way the government enrolled RSBY (non-study) eligible households into the program: via a mobile enrollment truck that visited each village. One difference is that we went to each household to ask them if they would like to enroll and took them to the enrollment truck, which was parked in one place in the village. By contrast, the government informed non-study households by delivering paper notices (chits) to each home about when and where the enrollment truck would be in the village.

Roughly 78.4%, 70.4% and 58.6% of households in arms A, B, and C, respectively enrolled in RSBY. Enrollment rates are somewhat higher in Gulbarga than Mysore: 77.9/76.4/64.1% v. 78.8/63.5/52.3% in A/B/C. No one in arm D enrolled.

For all study households that take up insurance, we paid the government their premiums. For households in arms A, this was funded by grant funds. For those in B and C that purchase insurance, this was funded by the respondents' money.

The Karnataka government renewed RSBY automatically for non-study and study households in 2016 and 2017 without any action—even payment—by enrollees. RSBY ended in the state on August 31, 2018, to make way for the new NHPS scheme, which is scheduled to start in late 2018 or early 2019. As of this writing, Karnataka had agreed to roll out NHPS but had not begun the roll-out.

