In addition, we will estimate two substantively different specifications to abstract away from methods of access to insurance and towards the mere fact of access to insurance. On one, we replace the four household group indicators with an indicator for whether the household was in group A, B or C and we replace the four village-level arm share variables with the share in groups A, B or C.¹¹ Additionally, we will estimate a specification where σ_j^v is replaced by the total share of the village eligible for RSBY, including both the share assigned to A, B and C as well as the share of the village with BPL cards or in certain eligible occupational classifications (who were therefore RSBY eligible).

Control variables. We first estimate a variant of the regression model above without any controls X_{ijs} , where s indicates a time that may not be equal to t . We then estimate a specification where X_{ijs} is a vector of baseline controls (i.e., X_{ijs} at time $s = 0$). We will use machine learning methods to select these control variables. Finally, we will run specifications where X_{ijs} may include so-called “coloring variables” that shed light on mechanisms of impact, welfare effects, and the dosage of treatment. In the latter case, we will include interactions of treatment variables with coloring variables, the same manner in which we estimate heterogeneous treatment effects. These coloring variables are listed in section 8.

Weighting. This regression can be weighted in multiple ways. We could either weight each household equally or weight each village arm identically. When examining household-level access We choose to weight each household equally because no household is obviously more informative than any other, especially when examining questions about the impact of insurance on households. When examining spillovers, we will weight villages equally.

Standard errors. We use the cluster robust HC2 standard errors at the village level. [name], Jiang, and [name] (2019) shows that this is a conservative variance in two-stage randomized experiments.

Spillovers. To address the possibility of spillovers from, e.g., giving some households access to insurance in one way affects households not given access to insurance in that way, we do a few things.

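### The supplementary pooled any-access model confounds the village access share with the A/B/C mix, so it can show a share effect on take-up when there is no spillover

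*Combined protocol and SAP*

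**What the plan says.** Section 7.1 (Coding treatment variables and the text after it) first sets out models that keep the household arms apart. It then adds a specification meant to set aside how access was given. In it, "we replace the four household group indicators with an indicator for whether the household was in group A, B or C". The village side is collapsed in the same way, to one variable holding the combined proportion assigned to any of the three access arms. A further version replaces the share with the total RSBY-eligible share of the village. Under Spillovers, the same section says that interactions between household arm and village arm will be left out when effects are reported at average spillover.

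On the design, Section 5.2 states: "The percentage allocations to the 4 household-level arms are given in the last 4 columns of Table 1". The rows that matter most here (village arm, % of villages, then % in A, B, C, D) include "III 15 30 10 10 50" and "IV 35 70 10 10 10", with overall row "Total 100 40 20 20 20".

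On whether the three forms of access act alike, Section 5.4 reports: "Roughly 78.4%, 70.4% and 58.6% of households in arms A, B, and C, respectively enrolled in RSBY". Nobody in D enrolled. Section 10 adds that group C used the RSBY card more at midline.

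The plan does not keep arm indicators in the pooled model, hold the mix constant, or warn that the pooled share term carries composition.

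**The concern.** The pooled share is meant to measure how many neighbours have access. Under Table 1 it also indicates which kind of access a typical access household has. If free and paid access act differently on an outcome, that difference loads on the share terms even when no household is affected by its neighbours.

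Spillover is one of the plan's evaluation questions and the reason for the two-stage design. A non-zero share coefficient from this model would naturally be read as spillover. Take-up is at once the outcome with known arm differences and one that Section 7.1 names for spillover testing. Section 11.2 also plans a main effect of insurance penetration for all groups together, which has the same weakness if it is run in pooled form.

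**Working it through.** **Inputs.** Village and household allocations from Table 1; uptake of 78.4/70.4/58.6% in A/B/C and 0% in D (Section 5.4). Assumptions: equal village sizes, so household and village weighting agree, and zero spillover, so a household's expected outcome depends only on its own arm.

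**Table 1 check.** A: 0.15×30 + 0.15×30 + 0.15×30 + 0.35×70 + 0.20×10 = 40%. B, C and D each come to 20%. Applied to the total target of 11,250, this gives the stated 4,500 and 2,250 per arm.

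**Mix and implied uptake by village arm.**

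| Village arm | % villages | Access share | A:B:C among access | Pooled uptake |
|---|---|---|---|---|
| III | 15 | 0.5 | 3:1:1 | 72.8% |
| V | 20 | 0.7 | 1:3:3 | 66.5% |
| I | 15 | 0.9 | 3:5:1 | 71.8% |
| II | 15 | 0.9 | 3:1:5 | 66.5% |
| IV | 35 | 0.9 | 7:1:1 | 75.3% |

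For example, III is (3×78.4 + 70.4 + 58.6)/5 = 72.8 and V is (78.4 + 3×70.4 + 3×58.6)/7 = 66.5. Arms I, II and IV together give (15×71.8 + 15×66.5 + 35×75.3)/65 = 72.5% at share 0.9, with a mix of 57.3/21.4/21.4.

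**Interacted pooled model.** The access-by-share coefficient is the slope on share among access households minus the slope in D, which is 0.
- Access-household weights at 0.5, 0.7, 0.9: 0.15×0.5 = 0.075; 0.20×0.7 = 0.140; 0.65×0.9 = 0.585. Mean share = 0.662/0.8 = 0.8275.
- Sxx = 0.075×0.3275² + 0.140×0.1275² + 0.585×0.0725² = 0.013395.
- A's part of the mix departs from its mean of 0.5 by +0.100, −0.357 and +0.073. Sxy = 0.075×(−0.3275)×0.100 + 0.140×(−0.1275)×(−0.357) + 0.585×0.0725×0.073 = 0.0070.
- Slope of A's part on share = 0.0070/0.013395 = 0.523. B and C have equal parts at every share, so each has slope −0.261.

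With tau as the effect of each arm relative to D, the slope under no spillover is **0.523·tauA − 0.261·(tauB + tauC)**, that is, 0.523 times the gap between A and the mean of B and C. For take-up the gap is 0.784 − (0.704 + 0.586)/2 = 0.139, so the slope is **+0.073 per unit share**. By district it is +0.040 in Gulbarga (gap 0.0765) and +0.109 in Mysore (gap 0.209). The share coefficient for D stays 0.

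**Model without the interaction.** Among D the weights are 0.075, 0.060 and 0.065, the mean share is 0.69, and Sxx = 0.00558. The common share coefficient is 0.0726 × 0.013395/(0.013395 + 0.00558) = **+0.051**. In this form the artefact is also attributed to D.

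**After correction.** With arm indicators added, or access households reweighted to 2:1:1 in every village arm, the share and interaction coefficients are exactly 0 and the any-access coefficient is 0.5×0.784 + 0.25×0.704 + 0.25×0.586 = 0.7145.

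**Could it be taken for a finding?** As an illustration, 150 trials were simulated per setting with 424 villages of 26 households, village-clustered robust standard errors (a CR1 stand-in for the planned HC2) and a two-sided 0.05 level. The level and the latent village ICC are assumed, since the plan gives neither. For take-up the interaction was falsely rejected in about 47%, 31%, 25% and 18% of trials at ICC 0, 0.05, 0.10 and 0.20. With arm indicators the rate was 3–7%. Monte Carlo error is about 2–4 points.

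**An outcome where the arms differ little.** Assume hospitalization at a base rate of 5–20% and a 25% relative effect scaled by enrollment. The slope is then base × 0.25 × 0.139 × 0.523, or 0.001–0.004, and simulated rejection stays near 5%.

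**The case against.** The strongest reply is that the reach is narrow. Much of that stands.

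- A reader might infer that the Wald test for spillover rejects too often. The documents do not support this: the Section 7.1 test is written on village-arm terms with separate household arms, and no Wald test is specified for the pooled model. Equations (1) and (2) also keep the arms apart, and Section 11.1 compares village groups within a given household arm.
- A reader might infer that any difference among A, B and C creates a false slope. It does not. The slope is zero whenever A's effect equals the mean of B's and C's, however far B and C lie apart.
- A reader might infer a steady shift of mix with share, or a true contrast of 0.4 × 7.3 = 2.9 points between shares 0.5 and 0.9. The mix is nearly the same at those two shares, and implied uptake is 72.8% and 72.5%. The positive slope comes from fitting a line through a dip at 0.7. The 33% versus 78% contrast in A's part lies within share 0.9.
- A reader might infer that spillover onto controls is distorted throughout. In the interacted form D's share coefficient is unaffected; only the form without the interaction carries the artefact over to D.

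It is also fair to say that restoring arm indicators could undo the purpose of pooling. With A as reference, the access coefficient would become A's effect. Centring the indicators avoids that.

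What remains is that a pre-specified model, run as written, returns a non-zero share term on take-up under no spillover.

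**Conclusion.** The concern holds for the supplementary pooled model, and for the Section 11.2 penetration effect if that is run in pooled form. On take-up the false slope is +7.3 points per unit share with the interaction and +5.1 on the common share term without it. RSBY card use could be affected too, given the midline difference in group C, but the plan gives no figures from which to size it. Where the arms differ little the distortion is small. The version using the total eligible share has the same weakness, of a size that cannot be computed because village BPL and occupational shares are not given.

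The slopes rest on Table 1, the reported uptake, equal village sizes and zero spillover. The rejection rates rest further on the assumed level and ICC. The arm-specific models and their spillover test stand as written.

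**What to change.** In the pooled specification, and in the Section 11.2 penetration effect if pooled, keep the any-access indicator T, the share and their interaction, and add T×(1{B} − 0.25) and T×(1{C} − 0.25). Centring on the 2:1:1 mix keeps the any-access coefficient a pooled effect. The cost is two regressors and no new data.

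The indicators remove the artefact when arm effects do not themselves vary with the share. As a sensitivity check for that case, weight each access household by its target proportion (0.50, 0.25, 0.25) divided by its arm's proportion among access households in that village arm. Over the Table 1 cells, weighting by cell share, the sum of weights is 0.8 and the sum of squared weights is 1.204. The effective access sample is therefore 0.8²/(0.8 × 1.204) = 0.66 of its size. That loss, and the departure from the plan's equal household weighting, are reasons to keep it as a check only.

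State in the plan that neither step equalises the mix of access among a household's neighbours, which still differs by village arm, so the pooled share coefficient is not a pure penetration effect.

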7.1 Intent-to-Treat (ITT)

Our first parameter of interest is the ITT estimate of the impact of different forms of access to insurance (free, at cost, etc.). Our basic regression model to estimate this is:

$$y_{ijt} = \sum_{v=1}^5 \beta_v d_j^v + \sum_{h=1}^3 \gamma_h d_{ij}^h + \sum_{h=1}^3 \sum_{v=1}^5 \lambda_{hv} d_j^v d_{ij}^h + \delta X_{ijs} + e_{ijt} \quad (1)$$

where y_{ijt} is the outcome for household i in village j at time t ; d_j^v is the indicator for village group $v \in \{1, 2, 3, 4\}$, corresponding to I, II, III, IV and V village groups; d_{ij}^h is the indicator for household

group $h \in \{1, 2, 3, 4\}$; γ_h for $h \in \{1, 2, 3\}$ are ITT estimators for adding one household to groups A, B, and C (D is the baseline); and (β_v, λ_{hv}) measures spillovers.

Coding treatment variables. In order to facilitate interpretation of village group, we estimate an isomorphic specification that recodes the village groups variables, $(d_j^{v=1}, \dots, d_j^{v=5})$, to reflect share of village sample in arms A, B, C, and D, $(\sigma_j^1, \dots, \sigma_j^4)$. The mapping from village group indicators to arm shares is given by the last four columns of Table 1. So, for example, the indicator for village group 1, $d_j^{v=1}$, maps to $(\sigma_j^1, \sigma_j^2, \sigma_j^3, \sigma_j^4) = (0.3, 0.5, 0.1, 0.1)$. Our modified regression model is now:

$$y_{ijt} = \sum_{h=1}^4 \beta_h \sigma_j^h + \sum_{h=1}^3 \gamma_h d_{ij}^h + \sum_{h=1}^3 \sum_{h'=1}^4 \lambda_{hh'} \sigma_j^{h'} d_{ij}^h + \delta X_{ijs} + e_{ijt} \quad (2)$$

where σ_j^h is the proportion of group $h \in \{1, 2, 3\}$ or $\{A, B, C\}$ in village j . Unlike the nonparametric approach given in equation (2), this equation is based on a parametric assumption. However, this specification increases power as it has fewer parameters to be estimated and allows for extrapolation regarding the effects of varying treatment proportions (see Appendix E.1 of [name], Jiang, and [name] (2019)).¹⁰

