First, we measure ITT effects accounting for spillovers at the village level by examining the predicted effects on outcomes for a household in a given group at different shares of the village sample in that group. The specific shares selected could be in-sample shares or out-of-sample shares. We will highlight when we make out-of-sample predictions.¹² In cases where we want to report ITT under sample average spillovers, we will exclude interaction between household arms and, e.g., village arms.

Second, we make assumptions required for unbiased estimation of, (γ_h, λ_{hv}) with spillovers as given in [name], Jiang, and [name] (2019). The key assumption is partial non-interference, i.e., assignments in villages $j' \neq j$ do not influence outcomes in another village j .

Third, to test for the existence of spillover effects, we conduct the Wald test with the null hypothesis that $\beta_v = \beta_{v'}$ and $\lambda_{vh} = \lambda_{v'h}$ for any $v \neq v'$ and $h = 1, 2, 3, 4$. This test can be conducted for both take-up and any outcome variable of interest.

¹⁰<https://imai.fas.harvard.edu/research/files/spillover.pdf>.

¹¹Berry et al. (2018) consider different subsidies and associated extrapolation issues.

¹²Although our study varies the fraction of subjects in a village who receive access to insurance in some form, we do not – as Table 1 shows – give some treatment to no households or some treatment to all households. Therefore, to estimate the above parameter of interest we have to make out-of-sample predictions.

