7.4 Accounting for multiple inference

Access to health insurance may affect a number of aspects of households' lives (such as health behaviors, health outcomes, investment decisions, and so on). When testing hypotheses about the impact of treatment on individual outcomes, no multiple testing adjustment is required.

However, our survey instrument in many cases includes multiple questions related to a single behavior or dimension. When those multiple questions are used to test a common hypothesis about a behavior or dimension, an adjustment is required. We will account for multiple inference when testing such hypotheses by using indices of outcome variables and family-wise p -value adjustment.

To be more specific, we have listed in Section 8 the primary groups of outcomes that we intend to consider. For each of these groups, we will construct indices (à la Kling, Liebman, and Katz (2007)) of all the outcomes in the family taken together. Then, for each of these index outcomes, we will report both the standard p -value and the p -value adjusted for multiple hypothesis testing across all the indices. We will calculate the adjusted p -values using the step-down procedure of Hochberg (1988), which controls the family-wise error rate for all the indices. (This is the approach taken in, for instance, Banerjee et al. (2015).)¹⁴

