11.1 Estimation

We examine both the existence of spillovers and the mechanisms behind those spillovers. Our source of variation is the village-level group to which a household is indirectly allocated via the first stage of randomization. These analyses will take the form of examining whether outcomes (e.g., utilization, consumption, assets, health) and intermediating variables (e.g., incidence of gifts and loans, knowledge of RSBY, asset prices) within a given treatment assignment (groups A–D) differ according to the stratum to which the village was assigned.

We will estimate spillovers directly from our ITT and CATE analyses. Because both positive and negative spillovers are possible, we will use two-sided tests. We weight villages equally as that is the level at which we posit that spillovers occur.

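### Section 7.1 names no ITT model, evaluation point or control set as the source of the p-value that enters section 7.4, and equations (1) and (2) as printed leave the arm coefficients undefined

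*Combined protocol and SAP*

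**What the plan says.** Section 7.1 opens with model (1), introduced by "Our basic regression model to estimate this is". It crosses household arms with village-arm indicators, and the text calls the γ coefficients the ITT estimators for A, B and C against D. A recoding to village shares follows: "Our modified regression model is now", giving model (2). The plan then adds that "we will estimate two substantively different specifications to abstract away from methods of access to insurance". One of these pools A, B and C; the other uses the share of the whole village that is eligible for RSBY. Under Spillovers there is a further model: where an effect at sample-average spillovers is wanted, "we will exclude interaction between household arms and, e.g., village arms".

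Under Control variables, the order is "We first estimate a variant of the regression model above without any controls", then baseline controls picked by an unnamed machine-learning method, then versions with coloring variables interacted with treatment. Two things are fixed: equal household weights for household-level effects, and village-clustered HC2 standard errors.

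Section 7.4 says that "for each of these index outcomes, we will report both the standard" p-value and one "adjusted for multiple hypothesis testing across all the indices", by Hochberg's procedure. Tests on individual outcomes are left unadjusted. Neither section says which model or control set produces the p-value. Section 7.5 selects equation (2), but only for the attrition check.

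**The concern.** Hochberg's procedure protects a set of indices when each brings one p-value that was fixed in advance. It cannot account for a choice among several p-values made before the adjustment begins. Words such as basic, modified and first give an order of presentation, not a rule for deciding. The introduction says that the plan exists to commit to an analysis before endline data are obtained, and on this point it does not yet do so.

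The equations add to the problem. If γ_A depends on an unstated omitted term, two analysts who follow the same equation can report different quantities under the same name. At stake is whether a claimed A v D effect on an index carries the error rate that section 7.4 implies.

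**Working it through.** **Figures in the plan.** No type I error rate is stated, so there is none to reproduce. Two-sided testing is stated only for spillovers (section 11.1: "Because both positive and negative spillovers are possible, we will use two-sided tests"). I assume two-sided 0.05 throughout.

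**Inputs from the documents.** 11,089 households in 424 villages (11,089/424 ≈ 26 per village), and the Table 1 allocation. The sample-average shares reproduce:
- A: 0.15 × (30+30+30) + 0.35 × 70 + 0.20 × 10 = 13.5 + 24.5 + 2 = 40%.
- B: 0.15 × (50+10+10) + 0.35 × 10 + 0.20 × 30 = 10.5 + 3.5 + 6 = 20%. C and D are the same by symmetry.

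**Collinearity.** Leave the controls aside.
- Model (1): 5 village dummies + 3 arm indicators + 15 interactions = 23 columns. There are only 5 × 4 = 20 village-by-household cells, so the rank is 20.
- Model (2): 4 shares + 3 arm indicators + 12 interactions = 19 columns. The four shares sum to 1, and the rank is 4 × 4 = 16.
- In both, the interactions for a given arm add up to that arm's own indicator. This makes three redundancies, one per arm.

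**What γ_A then means.**
- Model (1), arm V interactions omitted: A v D in arm V villages only (20% of villages, with 10% of households in A).
- Model (1), arm I interactions omitted: A v D in arm I villages only.
- Model (2), D-share interactions omitted: A v D in a village with nobody in A, B or C. Table 1 has no such village.
- No-interaction model: an average of A v D over village arms.

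**Chance of a false positive.** Six independent tests would give 1 − 0.95^6 = 26.5%. These tests share data, so the two-stage design was simulated with no effect, using the sample and allocation above. OLS was used with village-clustered variance (CR1, close to HC2 with 424 clusters). Assumptions were ICC 0.03, control R² 0.05 or 0.20, and a continuous or 10% binary outcome. There were three scenarios of 100 designs × 60 outcomes. Treating the 6,000 replicates as independent, the Monte Carlo standard error at 20% is √(0.2 × 0.8/6000) ≈ 0.5 percentage points. Entries are the range over scenarios of P(at least one p < 0.05) for A v D.

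| Tests counted | All at sample-average shares | γ_A read directly |
|---|---|---|
| Models (1), (2), no-interaction; no controls | 8.3-9.4% | 14.8-16.0% |
| Same three models; without and with baseline controls (six tests) | 9.4-12.6% | 16.3-21.3% |

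A single specification had size 4.4-6.6%. One model run with both control sets gave 5.5-8.6%.

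Further null simulations agree. On the direct reading, the six tests gave 19% (ICC 0.02, R² 0.1) and 21% (ICC 0.05, R² 0.2). A separate run gave about 21% directly and about 11% at the sample-average mix. The z statistics of the three models correlate about 0.15-0.4 when γ_A is read directly, but 0.88-0.97 when all are evaluated at sample-average shares.

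**The case against.** The strongest reply is that the direct reading is a worst case. The Spillovers text in section 7.1 describes ITT effects as predictions at chosen shares, with out-of-sample predictions flagged. It gives the no-interaction model a role: effects at sample-average spillovers. On that basis the three models nearly duplicate one another and the six tests give about 9-13%. This stands, and it rules out quoting 20% as the single size of the problem. It does not close the gap. The same text leaves the shares open, in-sample or out-of-sample, and the definition under model (1) does call γ the ITT estimator.

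The intended coding of (2) can also be guessed: its definition line lists only A, B and C, and equation (4) in section 7.3 carries three shares and an intercept. But that coding puts γ_A at a village wholly in D, and it says nothing about (1).

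A reader might also infer a rate near 27% by counting the pooled-access model. That model has no arm A coefficient and answers a separately stated question. Likewise, the coloring-variable versions are described as mechanism analyses. Neither is counted here. Weighting and standard errors are fixed and add no choice for A v D.

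**Conclusion.** The concern holds in a limited form. No deciding analysis is named, and (1) and (2) do not define γ_A as printed. For one outcome and A v D, the null chance of at least one significant result among the six tests is about 9-13% at sample-average shares and 16-21% on the direct reading, against about 5% for one named analysis. These figures are mine, not the sponsor's. They assume two-sided 0.05, ICC 0.02-0.05 and control R² 0.05-0.2. Most of the excess comes from the model and evaluation point: adding baseline controls to one model only moves 5% to about 6-9%.

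A reader might infer that the models generally disagree, or would give opposite conclusions on an index. The documents do not support that. The low correlations arise because the direct coefficients estimate different quantities, and the simulations show only that significance can differ. Nor does anything suggest an intention to select results.

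**What to change.** In section 7.1:
- Omit one reference village arm from the interactions in (1), and one reference share from those in (2), for each household arm. State what γ then means.
- Name one model, one evaluation point and one control set as the only source of the p-value that enters section 7.4. A suitable evaluation point is A-D, B-D and C-D at the sample-average village mix, with households weighted equally as the plan already says.
- Either the no-interaction model, which the plan already assigns to sample-average effects, or model (1) averaged over the village mix would serve. They need not weight the village arms identically, so the choice has to be stated.
- Machine-selected baseline controls can stay, provided the selection algorithm is fixed in advance.
- State the significance level and sidedness.
- Label the remaining models as supporting, spillover or mechanism analyses.

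The cost is wording only, provided the choice is made before endline outcomes are seen by arm. No analysis is removed. The small downside is that a result seen only in a supporting model can no longer be claimed as confirmed.
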